2.2. Rationale

The latest WHO recommendation to treat with 40 mg/kg was **not informed by PK/PD studies**; rather it relied solely on differences in cure and egg reduction rates. Despite the fact that an estimated 25 million children are treated with PZQ annually, only one very recent study conducted by co-PI [name] and co-investigator [name] has evaluated PK/PD among children of any age.⁷

The current recommended dose of 40 mg/kg is extrapolated from the relatively few PK/PD studies of healthy adults as well as adults with varying degrees of liver failure. Despite the known flaws of this approach, including evidence from quantitative pharmacological methods that an extrapolation approach does not achieve accurate pediatric dosing, this continues to define dosing regimens for children.^{8,9} This is of significant concern given the many differences in drug absorption, metabolism, and distribution among children compared to adults.¹⁰ A specific and relevant issue for this proposal is that weight alone does not capture age-dependent nonlinearities in drug metabolism.⁸ Specifically, body weight-normalized drug clearance in children exceeds that of adults for many drugs,¹⁰ suggesting children may require a higher dose per unit of bodyweight.

Concerns regarding the use of 40 mg/kg dosing are further highlighted by the PK/PD study conducted by Co-PI [name] in Uganda.⁷ In that study, 60 children aged 3-8 years living in an *S. mansoni* endemic region of Uganda were randomized to receive 40 versus 60 mg/kg of PZQ. Importantly, the investigators found that the total PZQ area under the curve was a significant predictor of both cure rate and egg reduction rate, while administered dose was not a significant predictor. **Figure III** demonstrates expected individual cure rates at two different weights for children aged 3-5 years as modelled in 5,000 patients. These models suggest that doses much higher than 40 mg/kg are necessary to achieve cure rates of 85% as recommended by the World Health Organization. This was particularly true for younger children. Specifically, it is likely that 80 mg/kg is necessary to achieve recommended cure rates.

[figure not shown]

Figure III Individual cure rate by different PZQ doses as modelled in 5,000 patients in scale 0.0 (total failure) 1.0 (complete cure) 24 days post single doses PZQ. Median weight for age were used to calculate the plots. Adapted from [name] et al ⁷

CONFIDENTIAL

Immunity in schistosome infections has been mainly studied in school-age children (SAC, ≥ 6 years old), and adults ¹¹, yet infection occurs early in preschool-age ¹². Immune responses in PSAC are therefore understudied and not understood. Infections in early life have potent effects on the infant's developing immune system and thus may determine later life outcomes including responses to childhood routine vaccinations. It is essential that these responses are probed and understood since PSAC is a vaccine-target population and a key age for establishing morbidity.

Recent modeling of the impact of *S. mansoni* vaccine and MDA to achieve morbidity control and transmission elimination suggests a combination of vaccination and MDA is needed to control or eliminate schistosomiasis ¹³. Lack of a pediatric formulation for PZQ and current treatment guidelines restrict research in this area leading to poor knowledge of immune responses promoted by treatment. It is important to profile immune responses following PZQ treatment of infants to inform future vaccine development/deployment that would include the PSAC.

2.3. Potential Risks and Benefits

2.3.1. Potential Risks

PZQ is safe in preschool children as evidenced by a large number of published studies. The investigators, however, recognize that the study population constitutes a vulnerable population of very young children. This vulnerable population is studied because the objectives are to understand the safety and efficacy of praziquantel, a drug that benefits people globally, in very young children. Currently, these children are not included in preventive chemotherapy campaigns due to lack of data with respect to optimal dosing, PK/PD, safety at varying doses, and efficacy. The two PIs for the planned trial are both pediatricians with significant experience leading pediatric studies of helminthiasis in LMICs.

The primary risk is exposure to a higher dose of praziquantel than is routinely given. This is necessary and informed by a study conducted by co-PI [name] that demonstrated that standard 40 mg/kg dosing in young children is likely too low given lower cure rates in this age group and that 80 mg/kg is the necessary dose based on modelling. Children experienced minimal side effects in that study at 60 mg/kg. Further, a 60 mg/kg dose has been routinely given for *S. japonicum* to children over the age of four. Finally, a study addressing treatment for *S. mekongi* employed a dose of 75 mg/kg (split 50/25 mg/kg over 4 hours) for children aged 10-15 years.¹¹

Three events were denoted “severe” (vomiting (2) and vertigo) in the 75 mg/kg dose group which had N = 45 children; no Serious Adverse Events as defined by death, life threatening event, need for hospitalization, or persistent morbidity/incapacity, were reported in either group. The reported rates of adverse events were slightly higher in the 75 mg/kg group than the 40 mg/kg comparison group. In a separate recently published study in Cote D’Ivoire, escalating doses of praziquantel (20, 40, 60 mg/kg) were examined in a cohort of children including pre-school age children (PSAC) aged 2-6 years.¹² Among PSAC, adverse events were mild with fewer adverse events observed three hours post-treatment compared to pre-treatment. Importantly, the number of adverse events was similar among the three praziquantel treatment doses, with fewer adverse events observed in the placebo-treated groups. Only mild expected adverse events were reported with the exception of one moderate grade adverse event 3 hours after the first praziquantel dose in one PSAC (diarrhea). No serious adverse events were noted at any dose. We will minimize risk by “admitting” children for observation with active and passive assessment for adverse events for 12 hours. We will also provide children with a meal to minimize side effects. **Finally, we will administer the 80 mg/kg dose as two doses of 40 mg/kg split over three hours.**

There is also a small risk to young children from blood draw, which is due to iron deficiency anemia as a blood draw removes red blood cells and iron. This risk is minimal given the small amount (7 – 12 ml) that will be drawn at each of three time points, representing 20 – 25 ml in a year. For the immunology study subpopulation, an extra blood draw of 7ml will be made at 4-week follow up time point. Very minimal risks are associated with venipuncture itself, which will be performed by trained medical personnel.

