1. *Screening* We propose to employ a two stage screening process. The first phase is a village - based survey to identify children who are infected using rapid point of care testing (urine Circulating Cathodic Antigen (CCA)). CCA provides a highly sensitive and efficient means to screen children, with high sensitivity demonstrated in young children.^{18,19 20,21} Two stool samples (taken on consecutive days) will also be collected from every child who is CCA positive prior to the start of the study, at four weeks +/-1 week after treatment, and at 12 months post-treatment to provide a measure of infection intensity. Fecal smears will be prepared from each sample in duplicate applying the thick Kato-Katz technique for the detection of *S. mansoni*, *S. japonicum* and soil-transmitted helminths. Mean egg counts per gram of stool (epg) will subsequently be calculated and three intensity categories will be considered for *S. mansoni* and *S. japonicum* infection: light (1-99 epg), medium (100 – 399 epg) and heavy (>400 epg) as per World Health Organization Guidelines.²²

The second phase of screening will occur at the field laboratories in Palo, Leyte, The Philippines and in Lake Albert, Uganda. Prior to study enrollment, each child will undergo a physical exam and medical history to determine eligibility. Children who are not eligible based on severe malnutrition (WHZ < -3.0), severe anemia (hemoglobin < 7.0 g/dL) or chronic medical condition as defined by a disease lasting longer than three months and impacting a child's daily function or normal activities will be excluded at this stage.²³

1. *Study visit 1/Baseline.* After determination of eligibility, subjects will be enrolled following all screening assessments. Both field stations have a patient intake area with private areas for consenting and physical examinations. At this visit, a small blood drawing catheter will be placed to minimize the number of times children need to have a needle stick. Blood will be drawn for baseline morbidity studies (5 ml). In depth measures of nutritional status will be made, and children will be randomized to receive either 40 mg/kg or 80 mg/kg of Praziquantel either annually or six-monthly (4 arms).

In addition, children will be randomly split into two groups, half will have an extra 7 ml of blood drawn at the time of the morbidity studies (N=150) for immunologic studies and half will take part in pharmacokinetic studies (N=150, further details below).

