7.3. Laboratory Based Screening, Enrollment/Baseline

Philippines site: If children are deemed eligible based on both screening phases, they will be “admitted” to the Palo Field Laboratory for 12 hours. There will be one medical technologist assigned to four children.

Uganda site: If children are deemed eligible based on both screening phases, they will be “admitted” to the Kabatereine Schistosomiasis Research Center in Buliisa District for 12 hours. There will be one nurse assigned to four children. Technical work in this phase will be performed by Ministry of Health personnel (Vector Control Division).

Phase two screening will take place at the field laboratories to ensure other inclusion/exclusion criteria are met prior to enrollment. Specifically, information will be provided which will detail the second phase of screening as well as the full procedures, and informed consent obtained. Phase two screening includes capture of weight and height to determine nutritional status (weight for height z-score), laboratory studies

to rule out severe anemia, physical examination and history to rule out a chronic medical condition that might make deem a child ineligible.

At both sites, the following activities will take place in **ALL** participants:

- History and physical exam
- Weight and height
- A catheter will be placed for blood draws
- Blood collection (5 mL) for complete blood count (CBC) and renal/liver toxicity measures. Serum will also be used for morbidity studies (EED biomarkers, iron biomarkers, and pro-inflammatory cytokines). Before discharge, another blood sample will be removed between 6 – hours after administration of the first dose of the study drug. This enables monitoring for possible toxicity.
- HIV testing and malaria testing
- Lactulose/Mannitol beverage. Children will take a small volume of a lactulose/mannitol at a dose of 2 ml/kg up to a maximum of 20 ml beverage as a measure of gut permeability and gut absorptive capacity and we will collect urine for 2 hours afterwards. They will fast 30 minutes before the lactulose:mannitol administration.
- Ultrasound scan for detection of schistosomiasis-related morbidity.
- **Stool** collection for parasitology by Kato-Katz if two stools not provided prior to enrollment, fecal calprotectin and fecal occult blood (performed on site).
- **PZQ** administration at the study assigned dose after a meal consisting of local foods.

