- Final blood collection (3 ml) for CBC, renal, and liver toxicity 12 hours post dosing (all participants)

To participants further randomly selected for pharmacokinetics and immunology sub-studies:

- At each site participants will be randomly allocated into two groups with different blood sampling frequency but similar overall volume (an extra 5 ml)
 - Pharmacokinetic sub-study:
 - In a sub-set of children (N= 150 in both sites) the indwelling cannula will be used to obtain four blood samples of approximately 1 ml for PK/PD studies at respective intervals. Participants who will be sampled for PK/PD studies **will not** participate in the immunology sub-study
 - Immunology sub-study:

- In a sub-set of children in Uganda, 7 ml of whole blood will be collected for immunology assays (such as flow cytometry, Luminex, ELISpot and ELISA).
- Participants who will be sampled for the immunology sub-study **will not** participate in the PK/PD study
- A subset of children without schistosomiasis will be recruited and will provide urine before and after ingesting lactulose-mannitol solution. Stool and 4ml of blood will also be taken for study of gut microbiota/EED biomarkers and morbidity markers.

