7.5. Follow up at 6 months

The following activities will take place at the respective research laboratory. This visit will take approximately three hours with no overnight admission. Technical work in this phase will be performed by Ministry of Health personnel (Vector Control Division).

- **Admission** weight, height, clinical history
- **Stool** collection for:
 - Calprotectin and fecal occult blood (performed on site).
- **Urine** collection and storage for future processing of CAA. This will allow for monitoring of re-infection in the cohort.
- **PZQ or Placebo** administration at the study assigned dose after a meal consisting of local foods and monitoring for AE post-treatment

- **Blood:** Five ml for morbidity studies including CBC, iron biomarkers, EED biomarkers, pro-inflammatory cytokines and further 7 ml from the sub-group of N=150 children who were selected at baseline for immunology assays (such as flow cytometry, Luminex, ELISpot and ELISA). Before discharge, another blood sample will be removed between 6 – hours after administration of the first dose of the study drug. This enables monitoring for possible toxicity.
- **Ultrasound** to determine possible changes in baseline morbidity patterns

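### Section 2.3.1 puts blood loss at 20–25 ml a year plus 7 ml for immunology children, but the draws listed for those 150 children add to 46 ml, and the section's own per-visit range does not give its annual total

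*Combined protocol and SAP*

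**What the plan says.** Section 2.3.1 names iron loss through blood sampling as a risk to these young children and calls it minimal. The support offered is the volume: 7–12 ml is the amount "that will be drawn at each of three time points, representing 20 – 25 ml in a year". For the immunology subset it adds a single item: "an extra blood draw of 7ml will be made at 4-week follow up time point".

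The visit descriptions list the following draws.

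- **Baseline, all children (section 7.3):** "Blood collection (5 mL) for complete blood count (CBC) and renal/liver toxicity measures", and later "Final blood collection (3 ml) for CBC, renal, and liver toxicity 12 hours post dosing (all participants".
- **Baseline, immunology subset (section 4.2.1):** "half will have an extra 7 ml of blood drawn at the time of the morbidity studies (N=150) for immunologic studies". Section 7.3 also gives 7 ml.
- **Baseline, PK subset (section 7.3):** four samples of about 1 ml.
- **Week 4 (sections 4.2.1 and 7.4):** 7 ml, immunology subset only.
- **Month 6 (section 7.5):** 5 ml from all children and a "further 7 ml from the sub-group of N=150 children who were selected at baseline for immunology assays", plus a post-dose safety sample with no stated volume.
- **Month 12 (section 7.6):** 5 ml from all children and 7 ml from the immunology subset.

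Section 7.3 introduces the two sub-studies as having "different blood sampling frequency but similar overall volume (an extra 5 ml", which does not match the 7 ml immunology draw listed a few lines later.

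**The concern.** The protocol identifies iron deficiency anaemia as the way in which blood sampling could harm these children, and volume is its main ground for calling that risk minimal. The children are 12–47 months old, section 4.2.1 describes their general health as poor, and section 5.2 excludes only haemoglobin below 7.0 g/dl. If the volume is understated for one group, ethics boards reading section 2.3.1 see a more favourable figure than the schedule supports. The immunology subset is the group to check, because section 2.3.1 names one extra draw for it while sections 4.2.1 and 7.3–7.6 list 7 ml at four visits.

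**Working it through.** **Step 1. Reproduce the stated figure from its own inputs.** Three time points at 7–12 ml give 3 × 7 = 21 ml to 3 × 12 = 36 ml. The lower end of 20–25 ml is reproduced approximately; the upper end is not. With the week-4 draw, an immunology child's stated total is 20 + 7 = 27 to 25 + 7 = 32 ml on the annual figure, or at most 36 + 7 = 43 ml on the per-visit figure.

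**Step 2. Add the listed draws (ml).** The first total uses stated volumes only.

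| | Core only | PK | Immunology |
|---|---|---|---|
| Baseline | 5 + 3 = 8 | 5 + 3 + 4 = 12 | 5 + 3 + 7 = 15 |
| Week 4 | 0 | 0 | 7 |
| Month 6 | 5 | 5 | 5 + 7 = 12 |
| Month 12 | 5 | 5 | 5 + 7 = 12 |
| **Total, stated volumes** | **18** | **22** | **46** |
| Adding a month-6 post-dose sample, assumed 3 ml | 21 | 25 | 49 |
| Adding also a second baseline post-dose sample, assumed 3 ml | 24 | 28 | 52 |

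The second assumption is there because post-dose sampling at baseline is described at 6–8 hours in section 4.2.1, with an incomplete time range in section 7.3, and at 12 hours later in section 7.3. These may be one sample or two.

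**Step 3. Try the readings that favour the plan (immunology child).**

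- Baseline sub-study extra of 5 ml instead of 7 ml: 46 − 2 = 44 ml.
- All post-dose samples left out: 3 × 5 + 4 × 7 = 43 ml.
- Both together: 43 − 2 = 41 ml. This requires dropping a draw that section 7.3 lists for all participants.

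Each of these exceeds 32 ml.

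**Step 4. Size of the gap, using 46 ml.**

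- Against the annual total: 46 − 32 = 14 ml to 46 − 27 = 19 ml.
- Against the per-visit maximum: 46 − 43 = 3 ml.
- Baseline visit: 15 ml against a stated maximum of 12 ml.
- Children affected: 150/600 = 25%. Section 7.3 places the sub-study in Uganda, where it would be 150/300 = 50% of the site.

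**The case against.** The strongest reply is that section 2.3.1 already discloses most of the volume. Its 12 ml equals 5 + 7, exactly what an immunology child gives at months 6 and 12, so the per-visit range appears to have been built with that subset in mind. On those figures the section allows 43 ml, and 46 ml is only 3/43 = 7% more. This stands as far as it goes: the main fault is that the annual figure does not follow from the per-visit figure beside it. It does not rescue the annual figure, which is the one a reader would carry away.

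Several stronger conclusions are tempting, and the documents do not support them.

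- **An understatement of up to 81%.** This is 49/27 = 1.81. It sets an assumed month-6 volume against the lowest annual figure and ignores the per-visit range.
- **A sub-study imbalance of 28 ml against 4 ml.** The equal-volume remark in section 7.3 sits in the baseline visit, so the fair comparison is at that visit: 5 ml against the listed 7 ml. A year of immunology draws should not be set against one PK visit.
- **Definitive replacement figures of 46–49 ml a year and 15 ml per visit.** These presuppose one baseline post-dose sample and a 3 ml month-6 sample, neither of which is settled.
- **Parents were given a wrong total.** The consent form was not in the copy reviewed, and ethics boards also have the visit-by-visit volumes.
- **The risk is not minimal, or the haemoglobin outcome is biased.** The documents give no volume threshold. Iron is provided for anaemic children (sections 9.2.3 and 9.4). Sub-study allocation is random, so no difference between treatment arms is shown.

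**Conclusion.** The inconsistency is real and limited to the risk statement. The annual total in section 2.3.1 follows neither from its own per-visit range nor, for immunology children, from the listed draws. The 46 ml rests only on stated volumes. The 43–52 ml range reflects what the protocol leaves unclear, and even the stacked favourable reading of 41 ml stays above 32 ml.

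The stated total roughly fits core and PK children, at 18 and 22 ml, or 21 and 25 ml if the month-6 sample is 3 ml. If the baseline post-dose samples also prove to be two separate 3 ml draws, PK children reach 28 ml and pass it slightly.

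What has been shown is that the number supporting the word minimal is wrong for a quarter of the trial. It has not been shown that the volume is unsafe. No endpoint, analysis or sample size is affected.

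**What to change.** 1. Settle the draw schedule: the baseline sub-study volume (5 ml or 7 ml, sections 4.2.1 and 7.3), the number and timing of baseline post-dose samples (sections 4.2.1 and 7.3), and the volume of the month-6 post-dose sample (section 7.5).
2. Rewrite the sentence in section 2.3.1 with per-visit and annual totals for core, PK and immunology children. If the listed volumes stand, the immunology total is at least 46 ml.
3. Reassess the minimal-risk statement against those totals, and say what it is judged against.
4. Check that any consent text uses the same figures.

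The cost is a text amendment and, where the consent wording changes, its review. The stated risk becomes less favourable for the immunology group.

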2.3.2. Known Potential Benefits

- 2.3.2.1. **Pediatric Care.** Children are likely to receive better pediatric care as many do not ever have a history and physical examination by a healthcare provider. Children will be examined by the study physician and be referred for care provided by the study as needed including iron and nutritional interventions. The same procedures will be followed for children at baseline and follow up.
- 2.3.2.2. **Parasitological results and treatment.** For all screened children, parents will be provided with results of stool screening for both schistosomiasis and soil transmitted

helminths, which is not part of standard care in the study area. For all schistosomiasis infected children recruited into the main study, we will provide praziquantel (40 or 80 mg/kg at baseline and 12 months after treatment if re-infected) with half of the children receiving a second dose at six months. In addition, albendazole treatment will be provided at baseline for children infected with soil-transmitted helminths and again at 12 months post-treatment if they are re-infected.

3. OBJECTIVES AND OUTCOME MEASURES

3.1. Study Objectives

3.1.1. Primary

To assess the efficacy of PZQ administered at different dose regimens.

- 3.1.1.1. To measure drug efficacy as per standard parasitological endpoints (Cure Rate and Egg Reduction Rate) at 4 +/- 1 weeks post-PZQ.

3.1.2. Secondary

To assess the **safety and** efficacy and PK/PD of PZQ administered at different dose regimens.

- 3.1.2.1. To evaluate the PK/PD of both PZQ enantiomers given the concern that this has varied in studies of *S. mansoni*.
- 3.1.2.2. To expand PD endpoints for drug efficacy to include state-of-the art antigen tests to accurately capture residual worm burden (Circulating Cathodic and Anodic Antigens (CCA and CAA)).
- 3.1.2.3. To assess the safety and impact of PZQ treatment (dose and interval) on key measures of morbidity 6 and 12 months after initial treatment and mechanisms mediating morbidity
- 3.1.2.4. To further evaluate the safety of higher PZQ dosing (80 mg/kg) including bone marrow, renal, and liver toxicity as captured before dosing and 12 hours after.
- 3.1.2.5. To evaluate the impact of different doses (40 vs. 80 mg/kg) and varying dosing intervals (every 6 or 12 months) on iron status, hemoglobin, and age and gender adjusted longitudinal growth and nutritional status as captured by height and weight for age, and weight for height z-scores as determined by WHO Anthro.
- 3.1.2.6. To evaluate the mechanistic role of *Environmental Enteric Dysfunction (EED)* in the pathogenesis of schistosomiasis related morbidities. We will capture state of the art biomarkers of EE including fecal calprotectin, urine lactulose:mannitol ratio, serum

endotoxin, serum endotoxin core antibody, and pro- inflammatory cytokines and employ Path Modeling techniques to identify mechanistic pathways.

- 3.1.2.7. To assess the role of Environmental Enteric Dysfunction (EED) in inter-individual variability in PZQ area under the curve (AUC) PK parameters demonstrated in this age group.
- 3.1.2.8. To explore immune responses to *S. mansoni* infection and treatment
- 3.1.2.9. To assess the prevalence and the pattern of schistosomiasis-related morbidity as determined by ultrasound scan.

